9.2.6 Summary of Efficacy Analysis for the Primary and Key Secondary Endpoints

Table 6 and Table 7 below provides the overview of the efficacy analyses for the primary and key secondary endpoints

Table 6. Summary of Efficacy Analyses for the Primary and Key Secondary Endpoints at Week 12

Efficacy Variables	Analysis Method
Primary Variables	

 • ACR50 response at Week 12^a • ACR20 response at Week 12^c 	
 • Point estimate and 95% CI of the response rate for each Upadacitinib dose group and the MTX group. The 95% CI will be based on normal approximation. • Point estimate, 95% CI and p-value for the treatment comparison between each Upadacitinib dose group and the MTX group, where the p-value is constructed using the Cochran-Mantel-Haenszel test adjusting for geographic region. Both nominal p-value and adjusted p-value through the graphical multiplicity procedure described in Section 9.2.5 will be provided. The 95% CI will be based on normal approximation. • Subgroup analysis. • Imputation: NRI for primary analysis and OC for sensitivity analysis • Analysis Set: FAS and Per Protocol Analysis Set as supportive analysis (NRI only).
Key Secondary Variables	

Binary Endpoints:
 
 • ACR20 response rate at Week 12^a • ACR50 response rate at Week 12^c • ACR70 response rate at Week 12^{a,c}; • Proportion of subjects achieving LDA based on DAS28 (CRP) ≤ 3.2 at Week 12^{a,c} 	
 • Point estimate and 95% CI of the response rate for each treatment group. The 95% CI will be based on normal approximation. • Point estimate, 95% CI and p-value for the treatment comparison between each Upadacitinib dose group and the MTX group using the Cochran-Mantel-Haenszel test adjusting for geographic region. Both nominal p-value and adjusted p-value (applicable for ranked key secondary endpoints) through the graphical multiplicity procedure described in Section 9.2.5 will be provided. The 95% CI will be based on normal approximation. • Imputation: NRI for primary analysis and OC for sensitivity analysis • Analysis Set: FAS

Table 6. Summary of Efficacy Analyses for the Primary and Key Secondary Endpoints at Week 12 (Continued)

Efficacy Variables	Analysis Method
Continuous Endpoints:	

 • Change from baseline in DAS28(CRP) at Week 12^{a,c} • Change from baseline in HAQ-DI at Week 12^{a,c} • Change from baseline in SF-36 Physical Component Score (PCS) at Week 12^{a,c} 	
 • LS mean and 95% CI within each treatment group and LS mean, 95% CI and p-values between each Upadacitinib dose group and the MTX group using ANCOVA model with treatment and geographic region as fixed factors and baseline value as covariate. Both nominal p-value and adjusted p-value through the graphical multiplicity procedure described in Section 9.2.5 will be provided. • Imputation: MI • Analysis Set: FAS

- a. US/FDA regulatory purposes.
- b. EU/EMA regulatory purposes.
- c. Japan/PMDA regulatory purposes.

Table 7. Summary of Efficacy Analyses for the Primary and Key Secondary Endpoints at Week 24

Efficacy Variables	Analysis Method
Primary Variables	

 CR as measured by DAS28(CRP) at Week 24^b 	
 Point estimate and 95% CI of the response rate for each Upadacitinib dose group and the MTX group. The 95% CI will be based on normal approximation. Point estimate, 95% CI and p-value for the treatment comparison between each Upadacitinib dose group and the MTX group, where the p-value is constructed using the Cochran-Mantel-Haenszel test adjusting for geographic region. Both nominal p-value and adjusted p-value through the graphical multiplicity procedure described in Section 9.2.5 will be provided. The 95% CI will be based on normal approximation. Subgroup analysis. Imputation and rescue handling: NRI for primary analysis and AO for sensitivity analysis Analysis Set: FAS and Per Protocol Analysis Set as supportive analysis (NRI only).

 Change from baseline in modified Total Sharp Score (mTSS) at Week 24^c 	
 LS mean and 95% CI within each treatment group and LS mean, 95% CI and p-values between each Upadacitinib dose group and the MTX group using ANCOVA model with treatment and geographic region as fixed factors and baseline value as covariate. Both nominal p-value and adjusted p-value through the graphical multiplicity procedure described in Section 9.2.5 will be provided. Imputation: Linear extrapolation and AO. Analysis Set: FAS and Per Protocol Analysis Set as supportive analysis.

Table 7. Summary of Efficacy Analyses for the Primary and Key Secondary Endpoints at Week 24 (Continued)

Efficacy Variables	Analysis Method
Key Secondary Variables	

Binary Endpoints:
 
 • Proportion of subjects achieving CR based on DAS28 (CRP) < 2.6 at Week 24^{a,c}; • ACR20/50/70 response rate at Week 24^b; • Proportion of subjects achieving LDA based on DAS28 (CRP) ≤ 3.2 at Week 24^b; • Proportion of subjects with no radiographic progression (defined as change from baseline in mTSS ≤ 0) at Weeks 24^{a,b,c}. 	
 • Point estimate and 95% CI of the response rate for each treatment group. The 95% CI will be based on normal approximation. • Point estimate, 95% CI and p-value for the treatment comparison between each Upadacitinib dose group and the MTX group using the Cochran-Mantel-Haenszel test adjusting for geographic region. Both nominal p-value and adjusted p-value (applicable for ranked key secondary endpoints) through the graphical multiplicity procedure described in Section 9.2.5 will be provided. The 95% CI will be based on normal approximation. • Imputation and rescue handling for non-mTSS endpoints: NRI for primary analysis and AO for sensitivity analysis. • Imputation for mTSS endpoints: Linear extrapolation and AO. Analysis Set: FAS
Continuous Endpoints:	

 • Change from baseline in DAS28(CRP) at Week 24^b • Change from baseline in HAQ-DI at Week 24^b • Change from baseline in modified Total Sharp Score (mTSS) at Week 24^{a,b} • Change from baseline in SF-36 Physical Component Score (PCS) at Week 24^b 	
 • LS mean and 95% CI within each treatment group and LS mean, 95% CI and p-values between each Upadacitinib dose group and the MTX group using ANCOVA model with treatment and geographic region as fixed factors and baseline value as covariate. Both nominal p-value and adjusted p-value through the graphical multiplicity procedure described in Section 9.2.5 will be provided. • Imputation for non-mTSS endpoints: MI • Rescue handling for non-mTSS endpoints: LOCF after rescue and AO for sensitivity analysis • Imputation for mTSS endpoints: Linear extrapolation and AO. • Analysis Set: FAS

- a. US/FDA regulatory purposes.
b. EU/EMA regulatory purposes.
c. Japan/PMDA regulatory purposes.

9.3 Additional Efficacy Analyses for Period 1

Additional efficacy endpoints are listed below and will be summarized for all visits (that measurements are collected) in Period 1 by randomized treatment groups:

- ACR20/50/70 response rates;
- Change from baseline in individual components of ACR response;
- Change from baseline in DAS28(CRP) and DAS28 (ESR);
- Change from baseline in CDAI and SDAI;
- Proportion of subjects achieving LDA or CR by DAS28(CRP), DAS28(ESR), Simplified Disease Activity Index (SDAI), and Clinical Disease Activity Index (CDAI);
- Change from baseline in morning stiffness (severity and duration);
- Proportion of subjects with change from baseline in HAQ-DI ≤ -0.3 and ≤ -0.22 respectively;
- ACR/EULAR Boolean remission;
- Change from baseline in EQ-5D-5L;
- Change from baseline in FACIT-F;
- Change from baseline in WPAI;
- Change from baseline in SF-36;
- Change from baseline in mTSS at Week 24 and Week 48;
- Proportion of subjects with no radiographic progression (defined as change from baseline in mTSS ≤ 0) at Week 24 and Week 48;
- Change from baseline in radiographic joint space narrowing and erosion scores at Week 24 and Week 48.

9.3.1 Analysis of non-mTSS-Related Endpoints for Period 1

For continuous variables, statistical inference at each visit will be conducted using analysis of covariance (ANCOVA) with treatment and geographic region as the fixed factors and the corresponding baseline value as the covariate. Only nominal p-values will be provided. For subjects who meet the rescue criteria defined by not achieving 20%

improvement in TJC/SJC (for Week 12 through Week 24), or subjects who meet the rescue switching criteria at Week 26 defined by not reaching CDAI CR and not achieving 20% improvement in TJC/SJC), data after rescue will be overwritten by LOCF for primary analysis. As observed (AO) data regardless of rescue will also be summarized using descriptive statistics.

For binary endpoints, frequencies and percentages will be reported for each randomized treatment group. Similar CMH analyses as for the primary endpoint will be conducted and only nominal p-values will be provided. For the primary analysis, non-responder imputation will be used. In addition, subjects who meet the rescue criteria of not achieving 20% improvement in TJC/SJC (for Week 12 through Week 24) or subjects who meet the rescue switching criteria at Week 26 defined by not reaching CDAI CR and not achieving 20% improvement in TJC/SJC will be treated as non-responders at visits after rescue. As observed (AO) data regardless of rescue will also be summarized using frequencies and percentages.

Plots by randomized treatment group over time will be provided for selected efficacy parameters including ACR20/50/70, LDA and CR by DAS28(CRP) and CDAI, and change from baseline in DAS28(CRP), HAQ-DI and pain.

For Week 24 reporting, this set of analyses will be presented up to Week 24.

9.3.2 Analysis of Additional mTSS-Related Endpoints for Period 1

For other mTSS-related endpoints at Week 24 and 48, analyses based on linear extrapolation and the AO analyses will be conducted on the FAS population. For Week 24 reporting, analysis of mTSS-related endpoints will be presented up to Week 24.

For change from baseline in joint space narrowing score and joint erosion score at Week 24, linear extrapolation analysis and AO analysis will be performed similarly as described in Section [9.2.1.2](#).

According to protocol, subjects who prematurely discontinue study drug between \geq Week 12 and \leq Week 16 or between \geq Week 36 and \leq Week 40 will have x-ray collected at the PD visit. All subjects who remain in the study at Week 24 will have x-ray collected at Week 24 visit, and all subjects who remain in the study at Week 48 will have x-ray collected at Week 48 visit. Available x-ray data will be assigned to the following analysis time points based on the analysis windows defined in [Table 3](#): Baseline, Week 12, Week 24, Week 36, and Week 48.

In the linear extrapolation analysis for Week 48 x-ray endpoints, the Week 48 data will be imputed via linear extrapolation for the following subjects: subjects who meet the rescue switching criteria at Week 26, subjects who prematurely discontinued study drug prior to Week 40, and subjects otherwise (i.e., not switched to a different study drug at Week 26, not discontinued study drug prior to Week 40) missing observed x-ray in the Week 48 window but have available x-ray at an earlier time point. For those subjects who have switched study drug and/or prematurely discontinued study drug, the most recent x-ray data collected at treatment switching or at discontinuation of study drug will be used for extrapolation. For subjects otherwise missing observed x-ray in Week 48 window, available x-ray in the most recent analysis window (prior to the Week 48 window) will be used for extrapolation.

In the AO approach, the observed Week 48 measurements will be used and attributed to the original randomized treatment groups regardless of treatment switching or study drug discontinuation.

Similar statistical inference approach as described in [Section 9.2.1.2](#) and [Section 9.2.3](#) will be used for Week 48 mTSS-related endpoints. Only nominal p-values will be provided.

9.3.3 Summary of Additional Efficacy Analysis for Period 1

Table 8 below provides the overview of the additional efficacy analyses for Period 1 to be performed on different endpoints by randomized treatment group. For Week 24 reporting, this set of analysis will be presented up to Week 24.

Table 8. Summary of Efficacy Variables and Corresponding Analyses for Additional Efficacy Analysis for Period 1 (By Randomized Treatment Group)

Efficacy Variables	Analysis Method
Additional Variables (Summarized at All Visits in Period 1)	

Binary Endpoints:
 
 • ACR20/50/70 response rate • Proportion of subjects achieving LDA and CR based on DAS28(CRP), DAS28 (ESR), SDAI, and CDAI criteria • Proportion of subjects with change from baseline in HAQ-DI ≤ -0.3 and ≤ -0.22, respectively; • Boolean remission; • Proportion of subjects with no radiographic progression (defined as change from baseline in mTSS ≤ 0) at Week 24 and Week 48. 	
 • Point estimate and 95% CI of the response rate for each treatment group. The 95% CI will be based on normal approximation. • Point estimate, 95% CI and p-value for the treatment comparison between each Upadacitinib dose group and the MTX group using the Cochran-Mantel-Haenszel test adjusting for geographic region. Only nominal p-values will be provided, and the 95% CI will be based on normal approximation. • Plots by randomized treatment group over time for selected endpoints • Imputation and rescue handling for non-mTSS endpoints: NRI; AO for descriptive statistics • Imputation and rescue-switching handling for mTSS endpoints: linear extrapolation and AO. • Analysis Set: FAS

Continuous Endpoints:
 
 • Change from baseline in individual ACR components • Change from baseline in DAS28 (CRP) and DAS28 (ESR) • Change from baseline in CDAI and SDAI • Change from baseline in morning stiffness (severity and duration) • Change from baseline in EQ-5D-5L • Change from baseline in FACIT-F • Change from baseline in WPAI • Change from baseline in SF-36 • Change from baseline in modified Total Sharp Score (mTSS) at Week 48 • Change from baseline in JSN and Erosion at Week 24 and Week 48 	
 • LS mean and 95% CI within each treatment group and LS mean, 95% CI and p-values between each Upadacitinib dose group and the MTX group using ANCOVA model with treatment and geographic region as fixed factors and baseline value as covariate. Only nominal p-values will be provided. • Plots by randomized treatment group over time for selected endpoints • Rescue handling for non-mTSS endpoints: LOCF after rescue; AO for descriptive statistics. • Imputation and treatment-switching handling for mTSS endpoints: linear extrapolation and AO. • Analysis Set: FAS

9.4 Long Term Efficacy Analysis

Assessments to evaluate long term efficacy (Period 1 and Period 2 combined) will be analyzed for the following measures at Weeks 2, 4, 8, 12, 16, 20, 24, 26, 28, 32, 36, 40, 48, every 12 weeks through Week 240, and Week 260/PD:

- ACR20/50/70 response rates;
- Change from baseline in individual ACR components;
- Change from baseline in DAS28 (CRP);
- Change from baseline in DAS28 (ESR);
- Change from baseline in CDAI and SDAI
- Proportion of subjects achieving LDA and proportion of subjects achieving CR based on DAS28 (CRP), DAS28 (ESR), SDAI, and CDAI criteria;
- Change from baseline in morning stiffness (severity and duration);
- Proportion of subjects with change from baseline in HAQ-DI ≤ -0.22 ;
- Proportion of subjects with change from baseline in HAQ-DI ≤ -0.3 ;
- ACR/EULAR Boolean remission at all visits
- Proportion of subjects with no concomitant corticosteroid use (among subjects with corticosteroid use at baseline).

Assessments to evaluate long term efficacy will be analyzed for the following measures at Weeks 12, 24 and 48:

- Change from baseline in EQ-5D-5L;
- Change from baseline in FACIT-F;
- Change from baseline in WPAI.
- Change from baseline in SF-36.

Assessments for the evaluation of radiographic changes in Period 2 will occur at Week 96, Week 192 and Week 260 (or Premature Discontinuation visit):

- Change from baseline in modified Total Sharp Score mTSS;

- Proportion of subjects with no radiographic progression (defined as change from baseline mTSS of ≤ 0);
- Change from baseline in radiographic joint space narrowing and erosion scores.

Analyses will be based on As Observed (AO) data. Descriptive statistics will be provided for each treatment group sequence as defined in Section 9.1. These include the number of observations, mean, standard deviation, and 95% CI for continuous endpoints; and frequencies and percentages with 95% CI using normal approximation for binary endpoints. In addition, longitudinal analysis will be performed using MMRM or GLMM as described in Section 9.1.1 for the "non-switcher" sequences (as defined in Section 9.1) for all endpoints except radiographic endpoints and proportion of subjects with no concomitant corticosteroid use. Point estimates and 95% CI from the model will be provided for each treatment group sequence.

Plot for each treatment group sequence over time up to Week 48 will be provided.

For Week 24 reporting, long-term efficacy analysis will be presented up to Week 48.

Table 9 below provides the overview of the long-term efficacy analyses to be performed on different endpoints.

Table 9. Summary of Efficacy Variables and Corresponding Analyses for Long Term Efficacy Analysis (By Treatment Group Sequence)

Efficacy Variables	Analysis Method
Binary Endpoints:	

 • ACR20/50/70 response by visit • LDA and CR based on DAS28(CRP), DAS28 (ESR), SDAI, and CDAI criteria by visit • Boolean remission; • Proportion of subjects with no concomitant corticosteroid use (among subjects with corticosteroid use at baseline)* • Proportion of subjects with no radiographic progression (defined as change from baseline mTSS of ≤ 0) by visit* 	
 • Point estimate and 95% CI of the response rate for each treatment group sequence • Plot for each treatment group sequence over time up to Week 48 • Point estimate and 95% CI of the response rate using GLMM model for each "non-switcher" treatment group sequence (*endpoints excluded from this analysis) • Plot for each non-switcher treatment group sequence over time for key endpoints[#] • Imputation: AO • Analysis Set: FAS
Continuous Endpoints:	

 • Change from baseline in individual ACR components by visit • Change from baseline in DAS28 (CRP) and DAS28 (ESR) by visit • Change from baseline in CDAI and SDAI • Change from baseline in morning stiffness (severity and duration) by visit • Change from baseline in EQ-5D-5L by visit • Change from baseline in FACIT-F by visit • Change from baseline in WPAI by visit • Change from baseline in SF-36 by visit • Change from baseline in mTSS by visit* • Change from baseline in radiographic joint space narrowing and erosion scores by visit* 	
 • Point estimate, and 95% CI of mean change from baseline together with SD for each treatment group sequence • Plot for each treatment group sequence over time up to Week 48 • Point estimate and 95% CI of change from baseline using MMRM model for each "non-switcher" treatment group sequence (*endpoints excluded from this analysis) • Plot for each non-switcher treatment group sequence over time for key endpoints[#] • Imputation: AO • Analysis Set: FAS

Key endpoints for figures include: ACR20/50/70, LDA and CR based on DAS28(CRP) and CDAI criteria, Boolean remission, change from baseline in DAS28(CRP) and CDAI.

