4.2 Overall Study Design and Plan

This is a Phase 3 multicenter study that includes two periods and a Japan sub-study. Period 1 is a 48-week randomized, double-blind, parallel-group, active comparator controlled treatment period designed to compare the safety and efficacy of Upadacitinib 7.5 mg QD monotherapy (for subjects in Japan only), 15 mg QD monotherapy, and 30 mg QD monotherapy versus MTX monotherapy in adult MTX-naïve subjects with moderately to severely active RA. Period 1 is also designed to compare the efficacy of Upadacitinib 15 mg QD monotherapy and 30 mg QD monotherapy versus MTX monotherapy for the prevention of structural progression. Period 2 is a long-term extension to evaluate the long-term safety, tolerability, and efficacy of Upadacitinib (7.5, 15, or 30 mg QD) in subjects with RA who have completed Period 1. Starting with Amendment 5.01.01, subjects in Japan receiving upadacitinib 30 mg QD will be switched to upadacitinib 15 mg QD. For other countries, starting with Amendment 6, subjects receiving upadacitinib 15 mg and 30 mg QD will receive open label upadacitinib 15 mg QD and subjects receiving MTX will receive open label MTX.

The study is designed to enroll approximately 975 subjects at approximately 330 study centers worldwide to meet scientific and regulatory objectives without enrolling an undue number of subjects in alignment with ethical considerations. Therefore, if the target number of subjects has been enrolled, there is a possibility that additional subjects in screening may not be enrolled.

The study duration includes a 35-day screening period, a 48-week randomized, double-blind, parallel-group, active-comparator controlled treatment period (Period 1); a 212 week long-term extension period (blinded until the last subject completes the last visit of Period 1) (Period 2); and a 30-day follow-up (call or site visit).

Subjects will be randomized in a 1:1:1 ratio to treatment Groups 2, 3 and 4 below, except for subjects from Japan, who will be randomized in a 2:1:1:1 ratio to Groups 1, 2, 3 and 4:

- Group 1: Upadacitinib 7.5 mg QD monotherapy (subjects in Japan only; N = 75)

- Group 2: Upadacitinib 15 mg QD monotherapy (N = 300) (includes 37 subjects from Japan)
- Group 3: Upadacitinib 30 mg QD monotherapy (N = 300) (includes 37 subjects from Japan)
- Group 4: MTX monotherapy (N = 300) (includes 37 subjects from Japan)

Randomization is stratified by geographic region.

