9.0 Efficacy Analysis

9.1 General Considerations

There are three sets of planned efficacy analysis: analysis for the primary and key secondary endpoints (at Week 12 or Week 24), additional efficacy analysis for Period 1, and long-term efficacy analysis (Period 1 and Period 2 combined). All efficacy analyses will be carried out using the FAS population. For the Japan sub-study, efficacy analyses will be conducted for selected variables.

Period 1 Efficacy Analysis

This includes analysis for the primary and key secondary endpoints (at Week 12 or Week 24), and additional efficacy analysis for Period 1.

Standard efficacy analysis by randomized treatment groups (MTX, Upadacitinib 15 mg QD monotherapy, Upadacitinib 30 mg QD monotherapy, and additionally Upadacitinib 7.5 mg QD monotherapy for Japan sub-study only) will be performed on efficacy data up to Week 12. No protocol-defined background rescue medication or rescue switching will occur prior to the time point.

For visits at Weeks 16, 20, 24 subjects may have initiated background rescue medication due to lack of efficacy as evaluated by joint count criteria (i.e., not achieving 20%

improvement in both TJC and SJC compared with baseline at two consecutive visits). In addition, at Week 26 subjects may have switched to Upadacitinib + MTX combo treatment (rescue switching) that is different from their originally randomized treatment due to lack of efficacy as evaluated by CDAI and joint count criteria, jointly. For treatment group comparisons beyond Week 12 to the end of Period 1, appropriate approaches will be applied to assessments that occur after the time of such background rescue or rescue switching. For Week 24 reporting, this set of analyses will be presented up to Week 24.

Long Term Efficacy Analysis

Long term efficacy analysis (Period 1 and Period 2 combined) will be performed on As Observed data (defined in Section 9.1.1) by the treatment group sequences as described below. The treatment group sequences are grouped into "non-switchers" and "switchers" based on the protocol defined rescue at Week 26 (from MTX or upadacitinib to upadacitinib plus MTX).

"Non-switcher" sequences:

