1. MTX
2. Upadacitinib 15 mg QD
3. Upadacitinib 30 mg QD

"Switcher" sequences:

4. MTX → Upadacitinib 15 mg QD + MTX
5. MTX → Upadacitinib 30 mg QD + MTX
6. Upadacitinib 15 mg QD → Upadacitinib 15 mg QD + MTX
7. Upadacitinib 30 mg QD → Upadacitinib 30 mg QD + MTX

For Japan sub-study, there are three additional treatment sequences:

8. Upadacitinib 7.5 mg QD
9. MTX → Upadacitinib 7.5 mg QD + MTX
10. Upadacitinib 7.5 mg QD → Upadacitinib 7.5 mg QD + MTX

There will be no statistical testing; only descriptive statistics and confidence intervals will be provided. For Week 24 reporting, this set of analyses will be presented up to Week 48.

Starting with Amendment 5.01.01 (for Japan) and Amendment 6 (for global), subjects receiving upadacitinib 30 mg QD will be switched to upadacitinib 15 mg QD. For long term efficacy analysis, subjects will continue to be summarized under the treatment sequences as described above, regardless of dose switch – i.e., for treatment sequences 3, 5 and 7, data collected after dose switch will continue to be summarized under the same treatment sequences. The visit at which dose switch occurs could be different for each subject. The first and last visits at which dose switch occurs will be noted in the summary.

Global Analysis versus Japan Sub-Study

The primary and key secondary endpoints and the subsequent multiplicity control are only applicable for global analysis for subjects randomized to MTX, Upadacitinib 15 mg QD and Upadacitinib 30 mg QD - they do not apply to Japan sub-study.

For Japan sub-study, no multiplicity adjustments will be applied and only nominal p-values will be provided for all efficacy analyses. In addition, model adjustment for region will not be applicable for Japan sub-study. The nominal p-values for the mTSS-related endpoints in Japan sub-study should be interpreted with caution due to limited sample size.

Subgroup analysis for the primary endpoints is only applicable for global analysis as well. No subgroup analysis is planned for Japan sub-study due to limited sample size.

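### SAP 9.4's normal-approximation intervals break down in the smallest switcher sequences, chiefly in Japan, and at extreme response rates in Japan arms of 37 (minor)

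*SAP*

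**What the plan says.** SAP 9.4 analyses long-term efficacy on As Observed data at visits from Week 2 to Week 260. On who is summarised it says: "Descriptive statistics will be provided for each treatment group sequence as defined in Section 9.1". For response rates the summary is "frequencies and percentages with 95% CI using normal approximation for binary endpoints". It gives no minimum group size, truncation at 0% or 100%, or exact or score alternative. Table 9 repeats the plan but asks only for a point estimate and a 95% CI, without naming a method.

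The sequences in SAP 9.1 include subjects whose study drug changed at Week 26, for example "MTX → Upadacitinib 15 mg QD + MTX". SAP 9.1 adds: "For Japan sub-study, there are three additional treatment sequences". One of these is MTX to upadacitinib 7.5 mg plus MTX. Its general considerations also limit the Japanese output: "For the Japan sub-study, efficacy analyses will be conducted for selected variables".

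SAP 9.1 states that the long-term analysis has no testing, only descriptive statistics and confidence intervals. SAP 9.4 adds GLMM estimates with intervals for binary endpoints, but only in non-switcher sequences, and not for radiographic endpoints or for absence of corticosteroid use.

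**The concern.** The Wald interval takes its width from the observed proportion. With no responders, or only responders, the width is zero. With one or two failures in a small group the upper limit passes 100%. In small groups it also covers the true rate less often than 95%, even away from the extremes.

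Some sequences are bound to be small, because Japanese MTX subjects who switch are divided among three upadacitinib doses. With neither tests nor model-based intervals for switchers, the printed interval is the only statement of how well their response is known. An interval of 100% to 100%, or one covering 71% of the time, overstates that knowledge.

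**Working it through.** SAP 9.4 states no figure of its own to reproduce, so the check is on how the prescribed interval behaves.

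**Inputs from the documents**
- Planned Japan arms: 75 on 7.5 mg; 37 each on 15 mg, 30 mg and MTX (SAP 4.2).
- Japanese MTX subjects who switch at Week 26 are re-randomised 1:1:1 (SAP 4.2).
- Planning response rates: ACR50 20% against 40%, remission 24% against 40%, ACR20 50% against 70% (SAP 4.3).

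**Ceiling on the Japan MTX-to-upadacitinib sequences.** If all 37 switched, each would hold 37/3 = 12.3, so about 12. Any lower switching share or any dropout gives fewer.

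**Other switcher sequences.** The documents give no counts. With an assumed switching share s of 5% to 40%:
- Japan MTX to upadacitinib, each: 37s/3 = 0.6 to 4.9
- Japan 15 mg or 30 mg to +MTX: 37s = about 2 to 15
- Japan 7.5 mg to +MTX: 75s = about 4 to 30
- Global MTX to upadacitinib, each: (300-37)s/2 + 37s/3 = about 7 to 58
- Global upadacitinib to +MTX: 300s = 15 to 120

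**Formulas**, with p = x/n and z = 1.96
- Wald: p ± z·√(p(1-p)/n).
- Wilson: [p + z²/2n ± z·√(p(1-p)/n + z²/4n²)] / (1 + z²/n).
- True coverage: the sum of binomial probabilities over all x whose interval contains the true rate.

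**Worked cases at n=12**
- True rate 50%: the Wald interval contains 50% only for x = 4 to 8. Coverage = (495+792+924+792+495)/4096 = 3498/4096 = 85.4%. Wilson: 96.1%.
- True rate 90%: the Wald interval contains 90% only for x = 8 to 11. P(x=12) = 0.9¹² = 28.2% and P(x≤7) = 0.4%, so coverage is 71.3%. Wilson: 97.4%.
- Upper limit above 100% needs x = 10 or 11: 23.0% + 37.7% = 60.7% at a true rate of 90%.

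**Coverage of the nominal 95% interval**

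| n | True rate | Wald | Wilson | Zero width | Outside 0-100% |
|---|---|---|---|---|---|
| 12 | 50% | 85.4% | 96.1% | <0.1% | 3.8% |
| 12 | 30% or 70% | 87.6% | 94.8% | 1.4% | 23.9% |
| 12 | 10% or 90% | 71.3% | 97.4% | 28.2% | 60.7% |
| 37 | 20-80% | 93.6-95.3% | 94.5-96.3% | ≤0.03% | ≤4.5% |
| 37 | 90% | 88.7% | 95.2% | 2.0% | 46.6% |
| 37 | 95% | 84.8% | 96.4% | 15.0% | 73.8% |
| 75 | 20-80% | 93.1-95.2% | 93.6-95.9% | about 0 | about 0 |
| 75 | 90% | 94.3% | 95.0% | <0.1% | 5.0% |
| 120 | 90% | 95.4% | 95.4% | about 0 | 0.2% |

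(The 20-80% rows span true rates of 20, 24, 40, 50, 70 and 80%.)

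**Example intervals, Wald then Wilson**
- 12/12: 100-100%, 75.8-100%
- 11/12: 76.0-107.3%, 64.6-98.5%
- 35/37: 87.3-101.9%, 82.3-98.5%
- 26/37: 55.5-85.0%, 54.2-82.5%

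**Zeros built in at Week 26.** A subject switches study drug only without CDAI remission and without 20% improvement in both joint counts. ACR20 requires that improvement in both counts (SAP 9.5.1). ACR20/50/70 and CDAI remission at Week 26 should therefore be 0/n in every switcher sequence, and Wald prints 0-0% at any n. Selection causes this zero, and no interval method makes it informative.

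**The case against.** The strongest case against is about reach and consequence, and much of it stands.

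- **Sizes.** A reader might infer that these intervals are wrong throughout the switcher and Japan output. The documents do not support that. At the stated Japan arm sizes and mid-range rates, Wald and Wilson nearly coincide. Global switcher counts are not given, and the two sequences that add MTX to upadacitinib could exceed 100. The design forces only the Japan MTX-to-upadacitinib sequences to be tiny.
- **Rates.** No source in the documents puts response near 100%. The planning rates run from 20% to 70%. Non-switchers also have GLMM intervals for ACR20.
- **Japan output.** Only selected variables are analysed there, so not every endpoint is affected.
- **Existing caution.** A reader might take the remark "should be interpreted with caution due to limited sample size" in SAP 9.1 as admitting this problem. It concerns nominal p-values for mTSS-related endpoints, not response-rate intervals.
- **Consequence.** The output is descriptive. Counts and percentages appear beside each interval, so a reader can see 12/12 for what it is.
- **Wording.** The SAP does not name a formula, and Wilson also rests on a normal approximation. Wald is the plain reading, not a certainty.

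These points limit the scope and make the matter minor. They do not remove it: at n=12, Wald under-covers even at a 50% rate, and the plan has no fallback. Elsewhere the SAP does guard against small groups: SAP 9.2.5, also using normal-approximation intervals, suppresses a subgroup variable if any category has fewer than 90 subjects. SAP 9.4 has no such rule.

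**Conclusion.** The concern holds for a limited set of cells. In the Japan MTX-to-upadacitinib sequences (at most about 12 each), in any other very small sequence, and at rates near 0% or 100% in Japan arms of 37, some intervals will have zero width, pass 0% or 100%, or under-cover. For Japan arms of 37 or 75 at rates of 20-80%, and for large global sequences, the prescribed interval is adequate.

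This rests on reading the prescribed method as Wald, on planned rather than actual Japanese enrolment, and on assumed true rates. As Observed denominators will shrink at late visits, which worsens the problem by an amount the documents do not give. No test, multiplicity step, or primary or key secondary result is affected. Severity: minor.

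**What to change.** In SAP 9.4, replace the normal-approximation wording with the Wilson score interval (or Clopper-Pearson) for single-group response proportions in all sequences. Name the same interval in Table 9, and state that it also applies to the Japan sub-study. Protocol 8.1.4.2 asks only for frequencies and percentages here, so the protocol text need not change. The current SAP version applies to future long-term reporting (SAP 11.1), which is the output concerned.

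The cost is one phrase and one software option. Intervals become asymmetric, and Clopper-Pearson is somewhat wider: 12/12 gives a lower limit of 0.025^(1/12) = 73.5%, against 75.8% by Wilson. Wilson is not perfect at the very smallest sizes (coverage 87.5% at n=4 and a 50% rate), which favours Clopper-Pearson if guaranteed coverage matters more than width. Week 24 reporting already presented this analysis up to Week 48, so final tables may differ slightly for the same visits. Re-run those tables or footnote the change of method.
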